#### **Study Treatment:**

The study medication, oxytocin, and its matching placebo will be purchased from Victoria Pharmacy in Switzerland and shipped to the MFA Investigational Drug Pharmacy via DHL Express or another express transportation service. Victoria Pharmacy will handle the packaging and shipping in accordance with the appropriate method required for the drug. The study medication will be received by and stored in the Investigational Drug Pharmacy and dispensing of study medication will be performed by a pharmacist in the Investigational Drug Pharmacy. The study is operating under FDA approved IND#120989. Patients will be administered oxytocin, 40 IU, or placebo (also a spray to be administered intranasal) within 1 hour prior to sleeping during the second sleep study. The PI will instruct the patient on how to use the spray, including how to prime the spray, and how to administer it.

#### **Benefits/Risks:**

There are no social/cultural, financial or legal risks to the subjects from participation in this study. No additional costs will be incurred to the patient or the institution as a result of this study.

Oxytocin nasal spray is relatively safe when used as directed. Side effects are extremely rare. The intranasal oxytocin dose is 40 IU. The oxytocin and placebo sprays will be compounded by Foer's Pharmacy in Bethesda, Maryland, and then shipped to our research pharmacy, Investigational Drug Services (IDS) Pharmacy, when it is prepared. IDS will store the oxytocin and placebo sprays according to the vendor's recommendations.

Some minor side effects may include: nasal irritation, runny nose, or tearing of the eyes, nausea and vomiting and an irregular heartbeat. Intranasal oxytocin is not FDA approved. Women of childbearing age who are not on a stable, reliable form of birth control will be excluded from the study.

It is acknowledged that there may be slight emotional discomfort associated with completing the consent form and participating in the research, but subjects are always free to drop out of the study if they encounter emotional discomfort.

In animal models of social stressors oxytocin has been shown to be protective against behavioral and cardiac dysfunction. For example social isolation, which increases heart rate, diminishes HR variability and vagal regulation of the heart, was prevented with oxytocin administration. Most pertinent to the hypotheses put forth in this proposal, the stress and increased anxiety in response to inhalation of 7.5% CO2 in healthy volunteers was prevented by intranasally administered oxytocin.

In addition, in human subjects, the evidence shows that intranasal oxytocin: (1) produces no detectable subjective changes in recipients, (2) produces no reliable side-effects, and (3) is not associated with adverse outcomes when delivered in doses of 18-40 IU for short term use in controlled research settings [ref 1]

Any data containing patient identifiers will be kept in separate files from the clinical data collected and will be stored in a secure location in the Division of Pulmonary, Critical Care and Sleep Medicine.

In order to make the oxytocin and placebo nasal sprays, Foer's Pharmacy needs to be provided with subject's personal information. We will need to provide the following to Foer's Pharmacy in order for subjects to participate in the study: Name, Date of Birth, Address, Phone Number and Drug Allergies. This information will only be used for purposes of making the drug, and it will not be released to any other parties, or to the subject's insurance company.

#### **Confidentiality:**

Individual research records will be stored securely in locked offices in the MFA Div. of Pulmonary, Critical Care and Sleep Medicine. They will be available only to study personnel. Individual records may be made available to personnel from The George Washington University Institutional Review Board for inspection purposes only. With this exception, individual records will be kept strictly confidential. The data will be stored until it has been analyzed and potentially used for publication purposes. Any publication of these data will not include personal identifiers.

As data is collected, subjects will be assigned a study identification number. Code break information (subject initials and subject medical identification number) will be stored in a separate file. Data files and the code break file will be password protected and files which contain any patient identifiers will be kept separate from the main data set.

#### **Costs to Subjects:**

There will be no additional costs to the subjects to participate in this protocol. The routine medical care for all tests and medications associated with the diagnosis and treatment of sleep apnea will be the responsibility of the patient.

#### **Subject Compensation:**

Subjects involved in this study will not receive any compensation.

#### **Statistical Considerations:**

ANOVA and Fisher's Exact Test will be done to compare multiple means from repeated measures. A consultation with an expert statistician will also be considered for data analysis.

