**Study Proposal:**

This proposal, based on the above detailed role of oxytocin in increasing parasympathetic and decreasing sympathetic cardiac control, will test if oxytocin administration blunts the deleterious hypoxia/hypercapnia induced changes in heart rate that occur during apnea in patients with OSA. This project will lay the groundwork and provide preliminary data to obtain NM funding to test this hypothesis more thoroughly and in larger clinical trials.

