#### **Cohort A: 10 Subjects**

1. 10 subjects that have recently undergone a standard "in the sleep-lab" diagnostic polysomnography (per standard of care medical guidelines, and not for research purposes) and have been diagnosed with OSA will be recruited into the research study to assess the beneficial effects of oxytocin treatment.
2. For research: These 10 subjects will undergo another "in the sleep-lab" diagnostic polysomnography that is identical to the one that they had for standard of care to diagnose OSA. This polysomnography that is performed for research will be funded externally by the investigating group.

*If subjects are female and of child bearing potential, then their birth control method for the duration of the study will be recorded, and a urine pregnancy test will be performed prior to the PSG.*

3. Within one hour prior to the research polysomnography the subjects will be given oxytocin 40 International Units, (IU) intranasally.
4. The following 4 outcome measurements will be compared between the two sequential diagnostic polysomnographies (initial without, and second with oxytocin) in the same subjects:
  - i. basal heart rate before sleep (primary outcome)
  - ii. mean changes in heart rate with apneic and hypopneic events (primary outcome)
  - iii. apnea-hypopnea index (secondary outcome)
  - iv. percentage of time spent by the patient with oxygen saturations: > 90%, > 80% but < 90%, and < 80% (secondary outcome)

The intranasal oxytocin dose is 40 IU. The drug will be stored in the Investigational Drug Pharmacy according to the vendor's recommendations.

Polysomnography (PSG) is a comprehensive recording of the biophysiological changes that occur during sleep. It is usually performed at night, when most people sleep, though some labs can accommodate shift workers and people with circadian rhythm sleep disorders and do the test at other times of the day. The PSG monitors many body functions including brain (EEG), eye movements (EOG), muscle activity or skeletal muscle activation (EMG) and heart rhythm (ECG) during sleep. After the identification of the sleep disorder sleep apnea in the 1970s, respiratory airflow and respiratory effort indicators were added, along with peripheral pulse oximetry.

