#### **Cohort B: 40 Subjects**

Once enrollment in Cohort A is complete, then enrollment into Cohort B will begin.

1. 40 Subjects that have recently undergone either a standard "in the sleep-lab" diagnostic polysomnography (per standard of care medical guidelines, and not for research purposes) or an "at home" PSG test and have been diagnosed with OSA will be recruited into the research study where we will assess the beneficial effects of oxytocin treatment.
2. For research: These 40 subjects will undergo an "in the sleep-lab" diagnostic polysomnography that would be identical to the one they had for standard of care medical guidelines if they were diagnosed with OSA "in the sleep-lab". This research

polysomnography should be performed within **4 weeks** of their OSA diagnosis PSG. This PSG that is being performed for research will be funded externally by the investigating group.

*If subjects are female and of child bearing potential, then their birth control method for the duration of the study will be recorded, and a urine pregnancy test will be performed prior to the PSG.*

3. Subjects will be randomized by the Investigational Drug Services Pharmacy of the MFA to be administered either Oxytocin (40 IU) or placebo within one hour prior to beginning the study polysomnography.
  - a. Both the polysomnography technician, the patient, and all research staff will be blinded to this randomization. The only un-blinded personnel will be the IDS pharmacy staff.
4. Subjects will then return within **4 weeks** to have a **second research study** polysomnography performed by the sleep-lab. This polysomnography that is being performed for research will be funded externally by the investigating group.
5. Subjects will be administered the intervention that *they did not receive* during the first research PSG study within one hour prior to beginning the second polysomnography. Either Oxytocin (40 IU) or placebo.
  - a. Both the polysomnography technician, the patient, and all research staff will be blinded to this randomization. The only un-blinded personnel will be the IDS pharmacy staff.

*For example: If at study polysomnography 1 a subject is randomized to receive placebo 1 hour prior to the start of the polysomnography, then at study polysomnography 2 the subject will be administered oxytocin (40 IU) 1 hour prior to the start of the polysomnography.*

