6. The following 4 outcome measurements will be compared between the two sequential diagnostic PSGs (initial standard of care without oxytocin, and second for research with oxytocin) in the same subjects:
  - i. basal heart rate before sleep (primary outcome)
  - ii. mean changes in heart rate with apneic and hypopneic events (primary outcome)
  - iii. apnea-hypopnea index (secondary outcome)
  - iv. percentage of time spent by the patient with oxygen saturations: > 90%, > 80% but < 90%, and < 80% (secondary outcome)

The intranasal oxytocin dose is 40 IU. The drug will be stored in the Investigational Drug Pharmacy according to the vendor's recommendations.

Polysomnography (PSG) is a comprehensive recording of the biophysiological changes that occur during sleep. It is usually performed at night, when most people sleep, though some labs can accommodate shift workers and people with circadian rhythm sleep disorders and do the test at other times of the day. The PSG monitors many body functions including brain (EEG), eye movements (EOG), muscle activity or skeletal muscle activation (EMG) and heart rhythm (ECG) during sleep. After the identification of the sleep disorder sleep apnea in the 1970s, respiratory airflow and respiratory effort indicators were added, along with peripheral pulse oximetry.

Inclusion Criteria:

- Men or women 18 years old or older of any ethnic background

- Subjects that have recently undergone a standard "in the sleep-lab" diagnostic polysomnography (per standard of care medical guidelines), or the "at home" diagnostic test for cohort B, and have been diagnosed with OSA will be recruited into a follow-up study to assess the beneficial effects of oxytocin treatment.

Exclusion Criteria:

- Pregnant or nursing women.
- Women at any child bearing age who are not willing to undergo pregnancy tests, and stable and reliable methods to prevent pregnancy
  - A female subject of childbearing potential is a non-menopausal female who has not had a hysterectomy, bilateral oophorectomy, or medically documented ovarian failure. Menopause can be assumed to have occurred in a woman when there is either:
    1. Appropriate medical documentation of prior complete bilateral oophorectomy  
OR

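### The only sentence naming an analysis method assigns Fisher's Exact Test to repeated-measures means, which it cannot compare; ANOVA is named beside it without a paired or crossover model

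*Combined protocol and SAP*

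**What the plan says.** The Statistical Considerations section has two sentences. The first names the methods: "ANOVA and Fisher's Exact Test will be done to compare multiple means from repeated measures". The second is "A consultation with an expert statistician will also be considered for data analysis", which commits to nothing. No other section names a test, model, contrast, significance level or interval.

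Both cohorts are within-subject:

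- **Cohort A** (10 subjects), item 4: "The following 4 outcome measurements will be compared between the two sequential diagnostic polysomnographies (initial without, and second with oxytocin) in the same subjects".
- **Cohort B** (40 subjects), items 3 to 5, is a two-period crossover: "Subjects will be randomized by the Investigational Drug Services Pharmacy of the MFA to be administered either Oxytocin (40 IU) or placebo" before the first research night, with the other treatment before the second. Item 6, however, words the comparison as "initial standard of care without oxytocin, and second for research with oxytocin) in the same subjects".

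The outcomes are the same in both cohorts. The primary outcomes are basal heart rate and mean heart-rate change with respiratory events. The secondary outcomes are the apnea-hypopnea index (AHI) and "percentage of time spent by the patient with oxygen saturations" in three bands.

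The Study Proposal says the study is to "provide preliminary data to obtain NM funding to test this hypothesis more thoroughly and in larger clinical trials".

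**The concern.** Fisher's Exact Test works on a table of counts from independent units. The plan has neither: every listed outcome is a measured quantity per subject and night, and the same subject supplies both sides of the comparison. The sentence therefore assigns the test a task it cannot perform. This is a wrong stated method, not merely a missing detail.

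ANOVA, named in the same sentence, can compare paired means. But nothing says that subject is a factor, whether period enters the Cohort B model, or which nights form the treatment contrast. A Cohort B subject can have three nights (diagnostic, oxytocin, placebo), so an analyst could put all three into one omnibus F-test. That test asks whether any night differs, not whether oxytocin differs from placebo.

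At stake are the power that a within-subject design should bring and the quantities a later trial would need: a treatment estimate, its confidence interval and the within-subject SD. The section promises none of them.

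**Working it through.** The plan states no alpha, SD, effect size, power or sample-size derivation, so there is no figure of its own to reproduce.

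**1. Does any listed outcome suit the test?**

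| Outcome | Type per subject and night | Table of independent counts? |
|---|---|---|
| Basal heart rate | continuous | no |
| Mean heart-rate change with events | continuous | no |
| AHI | index | no |
| Time in saturation bands | percentage of one patient's time | no |

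The last row is not a proportion of subjects. On the outcomes as defined, Fisher's test gives no p-value at all. It can be run only after an outcome has been turned into categories.

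**2. What if an outcome is dichotomised and the pairing ignored?**

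Assumptions, none from the documents: two nights, normal data with SD 1, two-sided 0.05, cut at the control mean, true shift 0 or 0.5 SD, within-subject correlation r.

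The paired analysis can be checked by formula. The SD of the difference is √(2(1 − r)). At r = 0.5 this is 1, so the standardised difference is 0.5, the noncentrality is 0.5 × √40 = 3.16 on 39 degrees of freedom, and power is 0.87.

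Simulation at n = 40 (10,000 trials per setting):

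| r | Type I error, paired | Type I error, Fisher unpaired | Power, paired | Power, Fisher unpaired |
|---|---|---|---|---|
| 0 | 0.055 | 0.033 | 0.59 | 0.34 |
| 0.5 | 0.047 | 0.008 | 0.87 | 0.31 |
| 0.8 | 0.049 | 0.001 | 1.00 | 0.27 |

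Here "paired" means the paired t-test, which equals two-night repeated-measures ANOVA. With a negative correlation of −0.3, the type I error of the unpaired Fisher test was 0.053 at n = 40 and 0.022 at n = 10. So this misuse is mainly conservative, and its cost is power.

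**3. What if three Cohort B nights enter one omnibus F-test?**

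Assume no drug effect, equal correlation between nights, and within-subject SD σ, so that a paired difference has SD σ√2. Let only the diagnostic night shift, by k paired-difference SDs, that is, by k√2σ. The squared deviations of the three means then sum to (2/3)(k√2σ)² = (4/3)k²σ², and the noncentrality is λ = n(4/3)k². With n = 40, the 5% critical value of F on 2 and 78 degrees of freedom is 3.11.

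| k | λ | Probability that F rejects |
|---|---|---|
| 0.2 | 40 × 1.333 × 0.04 = 2.13 | 0.23 |
| 0.3 | 40 × 1.333 × 0.09 = 4.80 | 0.47 |
| 0.5 | 40 × 1.333 × 0.25 = 13.33 | 0.90 |

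The oxytocin-placebo paired contrast stays at 5% throughout. A shift of the diagnostic night is plausible, since Cohort B admits subjects diagnosed at home while both research nights are in the laboratory. Its size is unknown.

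**The case against.** The strongest reply is that the sentence does name a usable method. ANOVA is stated to be for repeated measures, and with two nights that is the paired t-test, which suits the two-night comparisons in the outcome lists. This stands, and it means the plan is not without a valid test. It does not make Fisher's test appropriate, and it does not supply the missing model.

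A reader might infer that any p-value from Fisher's test in this trial would be wrong. The documents do not support that. A sequence-based form (Mainland-Gart, applied to within-subject preferences) is valid for a two-period crossover; its simulated type I error was at most 0.033 in every setting tried. The protocol also records gender, ethnicity and medical conditions, for which a between-subject Fisher test could be legitimate. The section mentions neither use.

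A reader might also infer inflated false positives from counting saturation epochs as independent observations. Nothing in the plan proposes counting epochs; the outcome is one percentage per patient and band.

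The three-night F-test is likewise a possibility, not a stated plan: the outcome lists speak of two sequential studies. The phrase about multiple means leaves it open, so step 3 is conditional.

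Finally, the study is exploratory and may consult a statistician. That lowers the stakes of any single p-value, but an optional consultation corrects nothing.

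**Conclusion.** The point holds in this form: the plan's only method sentence assigns Fisher's Exact Test to a comparison it cannot make, no defined outcome would suit it, and the accompanying ANOVA lacks a paired or crossover model and a treatment contrast. This rests on the text alone and needs no numerical assumption.

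The sizes are illustrations. At n = 40, correlation 0.5 and a 0.5 SD shift, dichotomising and ignoring the pairing would cut power from about 0.87 to about 0.31. The loss grows with the correlation, and the documents give no correlation. If, and only if, three nights were tested together, a diagnostic-night shift of 0.2 to 0.5 paired-difference SD would make the F-test reject 23% to 90% of the time with no drug effect.

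**What to change.** Replace the first sentence of Statistical Considerations with one paragraph:

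- **Fisher's Exact Test:** delete it, or tie it to a named categorical outcome with a method that respects the pairing (exact McNemar, or Mainland-Gart for the Cohort B crossover).
- **Cohort A:** for each outcome, the mean paired difference between the two nights with a 95% confidence interval.
- **Cohort B:** for each outcome, a linear mixed model on the two randomised research nights, with treatment and period as fixed effects and subject as random effect. Report the oxytocin-placebo contrast with a 95% confidence interval, and the within-subject SD. Other crossover models would also serve; the model and contrast must be stated.

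The Cohort B model departs from item 6 of that cohort's section, which compares the standard-of-care night with the oxytocin night. Say so openly, and reconcile item 6 with the randomised crossover in items 3 to 5.

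The cost is one paragraph and one corrected item, with no extra patients, nights or data. Written before unblinding, it also removes the choice of analysis after the results are seen.

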#### **Consent:**

Recruitment will occur through patient visits to the MFA, or through referrals from Walter Reed National Military Medical Center and DC Veterans Affairs providers. Introduction to the study will occur by face-to-face conversations with the subjects. The full study will be reviewed with a trained member of the research team in a private room. Subjects will be given the opportunity to ask questions and opt-out from the study during this conversation. If possible, written consent will be obtained then, but in order to avoid pressure or coercion, subjects will be provided the option to take the ICF home with them. If the subjects decide to participate they can either fax or scan and email a signed copy of the ICF to a member of the research staff. Then, either bring the wet-ink version, or wet-ink sign the ICF when they come in for their visit 1. The ICF needs to be signed prior to visit 1, as it is required for filling out the research drug prescription. During the subject's participation and during all collection and analysis activities, data will be assigned a unique study number and subsequently de-identified. No personal or demographic information

other than that specified in the study protocol will be acquired nor stored. A copy of the signed consent form will be provided to the patient

**Conflicts of Interests:**

None

